# Safety & Tolerability of Intraosseous Access for Hypertonic Saline Administration: A Pilot Study

## I. Objectives:

Question: Is it safe and tolerable to utilize intraosseous (IO) access in the ICU for hypertonic saline (HTS) administration?

Hypothesis: Utilizing the IO route for vascular access will be safe and tolerable for administration of hypertonic saline (3%) administration.

Operational definitions. Safety will be evaluated based on absence of extravasation of the infusion into the surrounding tissue and absence of tissue damage proximate to the IO infusion. Tolerability will be evaluated based on absence of pain severe enough that the patient requests the infusion be stopped or nonverbal indicators of pain such as agitation or pulling at the site.

## II. Background and rationale:

HTS is used to mitigate and temporize intracranial pressure (ICP) elevations and cerebral edema by creating an osmotic gradient across the cell wall. HTS is part of the elevated ICP algorithm in the emergency neurologic life support protocols (NCS, 2014). HTS is superior to mannitol which is the alternate osmotherapy agent (Kamel et al., 2011 & Ricard, et al., 2014). HTS is typically administered via central vascular access due to the concern that if extravasation of the infusion occurs, tissue damage from cell implosion can occur (Goutos, et al., 2014)

The IO route is generally accepted in resuscitation environments including the emergency department, EMS, and military settings with some authors recommending the IO as a primary method of obtaining emergency vascular access (Lewis & Wright, 2014). The adult advanced cardiac life support (ACLS) guidelines recommend either intravenous or IO access (Link, et al, 2015).

A number of studies have established the safety of IO administration of hypertonic solutions. Beberta, et al. (2014) randomized adult pigs to IO 7.5% HTS, IO 3% HTS, and 0.9% isotonic saline and found regular tissue morphology, no necrosis or microscopic ischemic changes in the HTS groups. Several studies conducted to evaluate the efficacy of hypertonic solutions on resuscitation for hemorrhagic shock used the IO route and did not make note of problems arising from the administration of IO HTS (Dubick, et al, 1992; Runyon et al., 1994). Another study using a canine model of hemorrhagic shock briefly mentioned transient lameness in the IO HTS group, but this resolved by 48 hours (Orasinski, Krahwinkel, & Sanders, 1992). While the majority of studies using hypertonic saline solutions did not make note of complications, one study induced hemorrhagic shock in dehydrated swine and resuscitated one group with 7.5% HTS and noted a high rate of local complications from soft tissue and bone marrow necrosis (Alam et al., 2002).

One study noted a subgroup of patients in which IO access was obtained on conscious patients (Schalk, et al., 2011). None of the patients received local anesthetic and none reported pain during insertion. Eighteen of the 22 conscious patients reported pain during fluid administration. Gazin, et al., reported all 5 conscious patients in their study reported pain with fluid administration (2001). Central venous catheter (CVC) placement is the current standard of care; even with

local anesthesia it can be painful. Most of the potential subjects, due to the nature of their severe neurologic injury, may not be affected by the pain associated with IO fluid administration. Manufacturer literature suggests the use of lidocaine to anesthetize the bone before infusing if possible (Teleflex).

It is expected that utilizing IO for vascular access in the ICU will be safe and tolerable. If this study confirms the anticipated results, there are numerous implications. First, neurologically injured patients requiring emergent HTS may have faster access to this therapy. A study comparing IO to CVC access undergoing resuscitation in the emergency department found IO to be faster to insert (2.3 vs. 9.9 minutes) and had fewer failures to access on the first attempt (Leidel, et al., 2009). Second, serious complications from IO were absent (Lewis & Wright, 2014) compared with severe to life-threatening mechanical complications from CVC including pneumothorax, damage to the carotid artery, and bleeding which were cited at 0.7%-2.1% depending on site (Parienti, et al., 2015). And thirdly, central line associated blood stream infections (CLABSI) are a leading cause of hospital acquired infections in the ICU and are associated with higher mortality (Lin, et al., 2015). CLABSI rates are measured by number of infections per 1,000 catheter days and shorter CVC dwell time is prudent. If a reliable and rapid source of vascular access could postpone or eliminate CVC insertion, risk of CLABSI may be reduced. These potential benefits outweigh the minimal expected risk.

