#### C. Measurements.

Outcomes

Primary outcome: safety

Secondary outcomes: tolerability

Data points

Absence of extravasation of the infusion into the surrounding tissue and absence of tissue damage proximate to the IO infusion

Pain scale (critical care pain observation scale) during insertion

Able to complete infusion without stopping for pain

Absence of nonverbal indicators of pain (CPOT)

Sodium:

Baseline serum sodium

2 & 6-hour post infusion serum sodium

Timing:

- Time of order for HTS
- Time of affirmative consent
- Time of start of IO procedure
- Time of successful IO placement (or failure to achieve access)
- Time until IO removed

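### Tolerability is met automatically by a patient who cannot feel or show pain, and no listed data point identifies such patients

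*Protocol*

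**What the plan says.** Section I (Objectives) states the hypothesis without restricting it by level of consciousness: "Utilizing the IO route for vascular access will be safe and tolerable for administration of hypertonic saline (3%) administration". The same section evaluates tolerability by "absence of pain severe enough that the patient requests the infusion be stopped or nonverbal indicators of pain", giving agitation and pulling at the site as examples of the latter.

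Section III.C (Measurements) ranks it: "Secondary outcomes: tolerability". Three data points serve it: "Pain scale (critical care pain observation scale) during insertion"; "Able to complete infusion without stopping for pain"; and absence of nonverbal indicators by CPOT, for which no time is stated. The remaining items are extravasation and tissue damage, serum sodium, and procedure times. Level of consciousness, sedation, and ability to report pain are not listed.

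Section II (Background and rationale) says of infusion pain: "Most of the potential subjects, due to the nature of their severe neurologic injury, may not be affected by the pain". It also cites a study of conscious patients in which "none reported pain during insertion. Eighteen of the 22 conscious patients reported pain during fluid administration".

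Entry is not limited by responsiveness. Section III.B admits any patient of the unit who fits the criteria, whatever the diagnosis, and section III.D accepts consent from the patient or from a surrogate.

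**The concern.** The outcome is defined by things that do not happen. In a patient who can speak or react, their absence is evidence about pain. In a patient with no behavioural response at all, it is not: no stop request can be made and no sign can appear, so the definition is met before the infusion starts. CPOT covers patients who cannot speak but still react. It does not separate a comfortable patient from an unreactive one.

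The protocol itself expects many subjects to be unaffected by the pain, but plans no item that would show who they are. If all five are recorded as having tolerated the infusion, a reader cannot tell how many of the five observations carry information about pain. The conclusion at stake is the tolerability half of the hypothesis, as it applies to patients able to report or show pain.

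Timing is a smaller, related gap. The pain reading with a fixed time is at insertion, where the cited study found none, and not at infusion, where it found most of it.

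**Working it through.** The protocol gives no target rate, precision or success threshold for tolerability, so there is no stated figure to reproduce. The check has two parts.

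**1. Can the definition fail in an unreactive patient?**
- Stop request by the patient: impossible.
- Nonverbal indicator (agitation, pulling at the site, CPOT behaviours): impossible if there is no behavioural response.
- Infusion stopped for pain: no trigger exists.

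All elements are met by construction. Going through the III.C list (extravasation and tissue damage, pain scale at insertion, completion, CPOT, sodium, times), no item marks such a patient. The time of consent is listed, but not who consented, so even that rough proxy is missing from the list.

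**2. How much does an all-tolerated result say, given the number who can be assessed?**

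Inputs: 5 subjects (section III.B). Let m be the number able to report or show pain; the protocol does not give it, so all values are shown. Let p be the failure rate among those m. Unreactive subjects contribute no failures, so

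P(no failures) = (1 − p)^m.

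Setting this equal to 0.025 gives the upper end of the exact two-sided 95% interval:

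upper limit = 1 − 0.025^(1/m).

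| m assessable | 0.025^(1/m) | Upper limit for p with zero failures |
|---|---|---|
| 5 | 0.478 | 52.2% |
| 4 | 0.398 | 60.2% |
| 3 | 0.292 | 70.8% |
| 2 | 0.158 | 84.2% |
| 1 | 0.025 | 97.5% |
| 0 | – | not estimable |

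The same five-out-of-five record is compatible with every row, and the listed data do not say which row applies.

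The chance of an all-tolerated result is not modelled here. That would need both the unreactive share and a failure rate, and the protocol gives neither. The Background's 18/22 = 81.8% and 5/5 are not usable as failure rates: they count any reported pain and not a request to stop. The 18/22 also had no local anesthetic, whereas this protocol gives lidocaine before the infusion.

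**The case against.** **The case mix is the target population.** The question concerns ICU use, recruitment is of neurocritical care patients for whom hypertonic saline is planned, and the Background discloses that many may not feel the pain. This stands in part: a statement about all five subjects is a valid description of that population. It does not cover patients who can feel pain. The protocol also expects some of these, since it allows the patient's own consent, as-needed lidocaine for pain, and a pathway for intolerable pain.

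**The III.C list may not be the whole data set.** It has no age, diagnosis or weight, although the lidocaine cap is per kilogram, and it omits the six-hourly sodium levels ordered in III.D. Charts will hold some related records. This is fair, but nothing commits the study to extracting a responsiveness reading or tying it to an infusion.

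**The scoring rule is inferred.** No per-patient score, proportion or threshold is defined. This stands as a caution. The definition by absence is nonetheless explicit, and an unreactive patient cannot fail it under any scoring.

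**Denominators and wording belong in a SAP.** That is true of the reporting. Which data are collected is a protocol matter, and an analysis plan cannot use a variable that was not recorded.

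**Five patients are uninformative anyway.** The 52.2% limit with all five assessable concedes this. The issue is that readers cannot tell whether even that much information is present.

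**Infusion pain is already captured.** Largely so: completion without stopping is recorded, and III.D acts on intolerable pain at any time in the study period. The timing gap is therefore small.

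**Conclusion.** The point holds as a minor one. As defined, tolerability cannot fail in a wholly unreactive patient. The protocol expects that most potential subjects may not be affected by infusion pain, and no listed item identifies them. An all-tolerated result could therefore partly reflect inability to feel or show pain.

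Size: the unreactive share is unknown. As illustration only, the upper limit with zero failures runs from 52.2% (five assessable) through 84.2% (two) to 97.5% (one), assuming independent patients with a common failure rate among those assessable.

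A reader might go further in three ways that the document does not support:
- That more than half the subjects will be wholly unreactive. The Background says only that most may not be affected by the pain, and patients who are nonverbal but reactive are covered by CPOT.
- That the difference between 52.2% and 84.2% measures a bias. The two limits refer to different populations: all subjects, and those able to show pain.
- That the description of all five is invalid, or that the study's main conclusion is compromised. The description remains sound for the unit's patients, and the primary outcome, safety, does not depend on pain behaviour.

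**What to change.** Add to section III.C, at each IO infusion:
- a level-of-consciousness or sedation score;
- concurrent sedatives and analgesics, as a descriptive record;
- a pain reading during the infusion, by self-report if the patient is able and otherwise by CPOT.

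Report tolerability for all five subjects and also, with its denominator, for those able to report or show pain. List the others as not assessable for pain, and limit the conclusion to match.

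The cost is a few data fields and a sentence in the outcome definition. The downside is a smaller assessable denominator, possibly zero, and so a less favourable tolerability statement. The primary outcome and clinical management are unchanged.

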### III. Procedures.

#### A. Research Design.

Prospective case series

#### B. Sample.

Potential subjects will be recruited when the determination by the neuroscience critical care unit (NCCU) care team is made to initiate HTS on a patient without a CVC/PICC. This pilot study will include 5 subjects. Potential subjects or their surrogate decision-makers will be approached by an investigator or assistant to request consent. Recruitment will be open to all NCCU patients fitting the above criteria regardless of primary diagnosis.

#### C. Measurements.

Outcomes

Primary outcome: safety

Secondary outcomes: tolerability

Data points

Absence of extravasation of the infusion into the surrounding tissue and absence of tissue damage proximate to the IO infusion

Pain scale (critical care pain observation scale) during insertion

Able to complete infusion without stopping for pain

Absence of nonverbal indicators of pain (CPOT)

Sodium:

Baseline serum sodium

2 & 6-hour post infusion serum sodium

Timing:

- Time of order for HTS
- Time of affirmative consent
- Time of start of IO procedure
- Time of successful IO placement (or failure to achieve access)
- Time until IO removed

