##### Exclusion criteria:

- <18 years old
- Known pregnancy
- Long bone fracture in the targeted site
- Proximity to prosthetic joint
- Excessive tissue/absence of anatomical landmarks
- Cellulitis over potential insertion site
- History of osteopetrosis

Investigators or assistants will request written or verbal telephone consent from the patient or surrogate decision maker if the patient is unable to consent. An IO will be inserted and placement confirmed by an inability to tilt the hub of the needle and the ease of flushing through the needle. 40 mg lidocaine will be slowly infused into the IO over 120 seconds, and then allowed to dwell for 60 seconds before infusing HTS. Repeat doses of 20 mg dose of lidocaine may be used as needed for pain to a cumulative maximum dose of 1mg/kg over the 24 hour study period. 3% HTS will be bolused through the IO in doses as prescribed per the NCCU team. Serum sodium level will be sent at 2 and 6 hours following the HTS bolus and every 6 hours. Repeat HTS boluses and/or continuous infusion may ordered per the NCCU team. Placement will be confirmed before and at the end of each bolus as above.

If at any time during the study period the patient has intolerable pain, a CVC or PICC will be placed and the infusion moved to the CVC/PICC. The IO will be removed.

If serum sodium is not appropriately rising following IO boluses, a CVC or PICC will be placed and further infusions will be moved to the CVC/PICC.

If extravasation occurs, a new IO will be placed at an alternate site and further monitoring and treatment will be determined.

The IO will be removed at or before 24 hours. If continued vascular access is required, a CVC or PICC will be placed.

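### No CPOT score is listed before IO insertion, so agitation already present is harder to attribute when tolerability is judged

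*Protocol*

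**What the plan says.** Protocol section I (Objectives, operational definitions) judges tolerability on two things. One is the absence of pain bad enough for the patient to ask that the infusion be stopped. The other is the absence of "nonverbal indicators of pain such as agitation or pulling at the site". Section III.C (Measurements) makes tolerability the secondary outcome and lists three pain-related data points:

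- "Pain scale (critical care pain observation scale) during insertion"
- "Able to complete infusion without stopping for pain"
- "Absence of nonverbal indicators of pain (CPOT", with no time given

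The same section lists "Baseline serum sodium" and two post-infusion sodium times. Its timing list runs from the HTS order to IO removal and contains no pain assessment. In III.D, the checks before and at the end of each bolus concern needle placement only.

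Section III.A describes a prospective case series, and III.B states "This pilot study will include 5 subjects". Section II says of pain from IO fluid administration: "Most of the potential subjects, due to the nature of their severe neurologic injury, may not be affected by the pain". III.D allows consent by a "surrogate decision maker if the patient is unable to consent".

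**The concern.** Agitation is an ambiguous sign in a neurocritical care patient, because it may precede the IO and have nothing to do with it. The protocol lets it count against tolerability but lists no record of the patient's state before the needle goes in. There is no comparator group to show how much agitation would be seen without an IO.

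Two errors are possible. Agitation that was already present may be read as IO pain, and a tolerant patient is counted as intolerant. Or IO pain may be put down to prior agitation, and an intolerant patient is counted as tolerant. Surrogate consent implies that some subjects may be unable to ask for the infusion to be stopped, and for them the nonverbal part carries more of the outcome. No later analysis can recover a score that was not taken.

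**Working it through.** The protocol gives no error rate, power, precision target or rate of prior agitation, so there is no planned figure to reproduce. The check is mainly of what is measured and when.

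**1. Is there a pre-IO reference?** The pain items in III.C are one score during insertion, one completion item and one CPOT item without a time. III.D adds none before insertion. So no pre-insertion score is listed.

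**2. Can the insertion score stand in?** It is taken while the needle is being placed, and before the IO lidocaine and the HTS described in III.D. A low score would give some reassurance. A raised score could reflect either the procedure or prior agitation. It is a measure of procedural pain, not a baseline.

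**3. Which parts of tolerability are exposed?**

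- A request to stop points to the IO directly: not exposed.
- Pulling at the site cannot predate the IO: not exposed.
- Pain that stops the infusion is recorded by the completion item: not exposed.
- Agitation and similar nonverbal signs that stop nothing: exposed.

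**4. Size of one error.** With n = 5, one misclassified patient is 1/5 = 20 percentage points, for example 4 of 5 tolerant instead of 5 of 5, or the reverse. In exact (Clopper-Pearson) 95% limits for the proportion failing:

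- 0/5: upper limit 1 − 0.025^(1/5) = 0.522, so 0% to 52%.
- 1/5: lower limit 1 − 0.975^(1/5) = 0.005 and upper limit 0.716, so 0.5% to 72%.

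The intervals overlap over most of their length, because 5 patients say little about a rate either way. What changes is the patient-level description, which is the main product of a case series.

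**5. Illustration on assumed rates.** Suppose a share p of patients is agitated before the IO, stays so, and is always counted as failing. The chance of at least one false failure among 5 is 1 − (1 − p)^5:

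- p = 0.10: 1 − 0.9^5 = 0.41
- p = 0.20: 1 − 0.8^5 = 0.67
- p = 0.30: 1 − 0.7^5 = 0.83

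The documents support none of these values of p. Counting every such patient as a failure is the extreme case, since staff may recognise prior agitation unaided. The conclusion does not rest on these figures.

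**The case against.** The protocol does not count agitation as such. It counts indicators of pain, so bedside staff already judge what a behaviour means. Section II suggests that many subjects may respond little to pain, and no section says candidates are agitated beforehand. The outcome is secondary, and no test, threshold or decision depends on 4 of 5 versus 5 of 5. The data-capture forms are not shown, and routine charting may hold earlier scores.

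Much of this stands. It limits the point to the attribution of one kind of sign, and it means that a pre-insertion score is not listed rather than known not to be collected. It does not remove the point: the bedside judgement still lacks a recorded reference, and the protocol neither mentions nor plans to use charted scores.

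A reader might infer three stronger things that the documents do not support:

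- *That prior agitation and IO pain cannot be separated at all.* Requests to stop and pulling at the site point to the IO by themselves.
- *That infusion pain goes unassessed because the CPOT item has no set times.* The item is an absence criterion. III.D acts on intolerable pain whenever it occurs in the study period and allows repeat lidocaine for pain, so ongoing assessment is presupposed. The missing times are mostly missing detail.
- *That the sodium baseline shows the CPOT plan to be inconsistent.* Sodium must be seen to rise, which needs a starting value, whereas CPOT here serves an absence criterion. The sodium entry shows only that the list names a baseline where one was wanted.

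**Conclusion.** The point holds in a limited form, as a cheap improvement and not a flaw that undermines the study. No pre-insertion CPOT is listed, and the one timed score is not a pre-IO reference. With no comparator, agitation already present is therefore harder to attribute. The possible effect is 1 of 5 per misclassified patient, in either direction. How often this would happen is unknown, because the documents give no rate of prior agitation.

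The conclusion assumes that the untimed CPOT item is meant for the infusion. That is the natural reading of its place in the list and of the operational definition, but it is not stated. The primary safety outcome is unaffected.

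**What to change.** Make three short edits:

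1. In III.C, add one CPOT immediately before IO insertion, and mention it in the III.D procedures.
2. In III.C, label the existing CPOT item as applying during HTS infusion. Keep the insertion score as a separate measure of procedural pain.
3. In the operational definition in section I, state that the nonverbal criterion is judged as new or increased indicators relative to the patient's own pre-insertion score. Report both scores for each patient.

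The third edit is needed because a baseline without a rule for reading it would leave the classification open. A fixed scoring timetable during infusion is not needed for this purpose.

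The cost is 1 extra score per patient, 1 × 5 = 5 in the study, plus the matching data-entry field. Sample size, doses and clinical rules do not change. The downside is one more bedside score in an urgent setting. Agitation that begins after the baseline for other reasons would still not be fully separated from IO pain. The score can be added only for patients whose IO has not yet been inserted.
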